#### 7.1 Schedule of Study Visits

An overview of the study visit and evaluations schedule is presented in Table 1. Detailed instructions to guide and standardize procedures across sites are provided in the VOICE SSP Manual available at www.mtnstopshiv.org. As indicated in the SSP Manual, all MTN-003B visits may be conducted as split visits.

Table 1: Schedule of BMD Substudy Visits and Evaluations
--

Procedure	Screening and Enrollment Visit	Semiannual Follow-up Visit (every 6 mo during VOICE participation and for 12 months after the VOICE PUEV)	VOICE PUEV / BMD Substudy ETV *
Informed Consent for BMD Substudy	Х		
Eligibility Determination	Х		
Reimbursement	Х	Х	
Schedule Next Visit	Х		
Collect Contraception History	Х		
Collect/Update Lactation History	Х		
Collection of medical history (if not done in VOICE or other study)		▲	
Collect concomitant medications (if not done in VOICE or other study)		▲	
Nutrition Assessment – Anthropometric (height and weight)**	х	Х	Х
Nutrition Assessment – Clinical (physical signs of malnutrition)	х	Х	Х
Nutrition Assessment – Dietary (food frequency questionnaire)	Х	Х	Х
Collect/Update Physical Activity History	Х	Х	Х
Urine Collection for Pregnancy Test (may be omitted if already performed as part of VOICE procedures on same day)	•	•	
Urine Collection and Storage for Exploratory Objective Testing of Excreted Phosphorus and Creatinine	х	Х	х
DXA of Spine and Hip	Х	Х	Х
Blood Collection and Serum Storage for Exploratory Objective Testing of Markers of Bone Turnover and Bone Mineral Metabolism	х	Х	Х

X required

▲ *if indicated* 

\*These procedures are performed at the VOICE PUEV or BMD Substudy ETV if either occurs at least 30 days after the last semiannual BMD Substudy follow-up visit

\*\* Height and weight measurements performed and documented for VOICE within 14 days (inclusive) of an MTN-003B visit may be used for MTN-003B

# 7.2 Screening and Enrollment Visit

Eligibility determination and enrollment may take place on the day of random assignment in VOICE, or up to 13 days after the date of random assignment in VOICE.

## 7.2.1 Administrative and Regulatory Procedures

• Informed consent for screening and enrollment

- Eligibility determination
- Reimbursement
- Schedule next visit (if applicable)

# 7.2.2 Anthropometric and Clinical Procedures

- Contraception history
- Lactation history
- Nutrition assessment anthropometric (height and weight) Note: Height and weight measurements performed and documented for VOICE within 14 days (inclusive) of an MTN-003B visit may be used for MTN-003B
- Nutrition assessment clinical (physical signs of malnutrition)
- Nutrition assessment dietary (food frequency questionnaire)
- Physical activity history
- Blood collection
- Urine collection

## 7.2.3 Laboratory and DXA Procedures

- Urine pregnancy test (may be omitted if already performed as part of VOICE Study procedures on same day)
- Urine storage for possible testing for levels of phosphorus and creatinine
- Serum storage for possible testing of markers of bone turnover and bone mineral metabolism
- DXA of spine and hip

## 7.3 Follow-up Visits

Follow-up visits will occur on a semiannual basis (approximately every 6 months) and may be completed on the same day as VOICE Study visits. The follow-up visits will occur at 6 months and 12 months following the VOICE PUEV. The semiannual follow-up visit procedures listed below will also be completed at either the VOICE PUEV or the BMD Substudy ETV if at least 30 days have passed since the last semiannual follow-up visit.

## 7.3.1 Administrative and Regulatory Procedures

- Reimbursement
- Schedule next visit, if indicated

## 7.3.2 Anthropometric and Clinical Procedures

• Update lactation history, if indicated

- Nutrition assessment anthropometric (height and weight) Note: Height and weight measurements performed and documented for VOICE within 14 days (inclusive) of an MTN-003B visit may be used for MTN-003B
- Nutrition assessment clinical (physical signs of malnutrition)
- Nutrition assessment dietary (food frequency questionnaire)
- Collection of medical history (if not done in VOICE or other study)
- Collection of concomitant medications (if not done in VOICE or other study)
- Physical activity history
- Urine collection
- Blood collection

#### 7.3.3 Laboratory and DXA Procedures

- Urine pregnancy test (may be omitted if already performed as part of VOICE Study procedures on same day)
- Urine storage for possible testing for levels of phosphorus and creatinine
- Serum storage for possible testing for markers of bone turnover and bone mineral metabolism
- DXA of spine and hip

## 7.4 DXA Scan

The most widely recognized test for measuring BMD is a quick, painless, noninvasive technology known as DXA. This technique, which uses low levels of x-rays, involves passing a scanner over the body while the individual lies on a cushioned table. DXA can be used to determine BMD of the entire skeleton and at various sites that are prone to fracture, such as the hip, spine, or wrist. BMD by DXA at the hip and spine is generally considered the most reliable way to classify osteoporosis, assess changes in BMD, and predict fracture risk.

To reduce measurement error, all DXA scans of the hip (total hip, femoral neck) and PA spine (L1-L4) will be performed in duplicate at each visit, and results will be recorded on case report forms. The SDMC will use this data to calculate the average of the two scans for a given visit. Use of the DXA scanner will follow standard protocols provided by the manufacturer.

Detailed instructions to guide and standardize all study procedures across sites will be provided in the VOICE SSP Manual, available at www.mtnstopshiv.org. The MTN will purchase identical scanners for each site, and appropriate training will be provided prior to implementation of the study according to International Densitometry Standards available at www.iscd.org/. The sites will follow routine daily QA protocols for the machine using a phantom and standard protocols. One of the study site phantoms will be sent to the second site for scanning to assess comparability of the two sites scans. The sites will routinely send (electronically) scans to the University of Pittsburgh Osteoporosis Center for QC.

## 7.5 Laboratory Evaluations

Evaluations will be conducted at local, regional, network, or approved reference laboratories according to guidelines outlined in the VOICE SSP Manual.

- Urine pregnancy test (done at local laboratories)
- Serum and urine will be collected and stored; these samples may be used for future measurement of markers of bone turnover and bone mineral metabolism and levels of excreted phosphorus and creatinine, respectively, if significant changes in BMD from baseline are observed following review of DXA scan results. The markers of bone turnover and bone mineral metabolism may include but are not limited to the following:
  - Bone turnover:
    - Bone resorption (CTX)
    - Bone formation (P1NP, BSAP)
  - Bone mineral metabolism:
    - Calcium
    - Albumin
    - PTH
    - 25-hydroxy vitamin D
    - Urine phosphorus and creatinine

#### 7.6 Follow-up Procedures for Participants who Temporarily Hold or Permanently Discontinue Study Product

Participants who temporarily hold or permanently discontinue use of study product will not routinely be withdrawn from this substudy. Rather, every effort will be made to complete all protocol-specified visits and procedures with these participants, except as noted below.

#### 7.6.1 Participants Who Become Pregnant

All protocol-specified study procedures will continue except for the following:

- DXA scan
- Collection and storage of urine and serum

These procedures may be resumed according to original schedule following completion of the pregnancy.

# 7.7 Specimen Collection and Processing

Each study site will adhere to the standards of good clinical laboratory practice, the HPTN-MTN Network Laboratory Manual (www.mtnstopshiv.org), DAIDS Laboratory Requirements (www3.niaid.nih.gov/research/resources/DAIDSClinRsrch/PDF/ labs/LabPolicy.pdf), VOICE SSP Manual (www.mtnstopshiv.org), and site standard operating procedures for proper collection, processing, labeling, transport, and storage of specimens at the local laboratory. Specimen collection, testing, and storage at the site laboratories will be documented when applicable using the Laboratory Data Management System (LDMS). In cases where laboratory results are not available due to administrative or laboratory error, sites are permitted to re-draw specimens.

# 7.8 Specimen Handling

Specimens will be handled in accordance with Requirements for DAIDS Sponsored and/or Funded Laboratories in Clinical Trials (http://www3.niaid.nih.gov/research/resources/DAIDSClinRsrch/PDF/labs/LabPolicy.pdf

# 7.9 Biohazard Containment

As the transmission of HIV and other blood-borne pathogens can occur through contact with contaminated needles, blood, and blood products, appropriate blood and secretion precautions will be employed by all personnel in the drawing of blood and shipping and handling of all specimens for this study as recommended by the CDC and NIH. All biological specimens will be transported using packaging mandated by CFR 42 Part 72. All dangerous goods materials, including diagnostic specimens and infectious substances, must be transported according to instructions detailed in the International Air Transport Association Dangerous Goods Regulations. Biohazardous waste will be contained according to institutional, transportation/carrier, and all other applicable regulations.

# 8 ASSESSMENT OF SAFETY

The BMD Substudy is an observational study involving no investigational products (beyond those in VOICE) or procedures associated with significant risk to participants. Therefore, few safety concerns are expected as a result of study participation. Safety monitoring specific to participation in this substudy includes reportable occurrences (as defined below) related to study participation and procedures, as well as results of DXA scanning.

# 8.1 Safety Monitoring

Site Investigators of Record (IoRs) are responsible for continuous close safety monitoring of all study participants, and for alerting the VOICE Protocol Team if

unexpected concerns arise. Safety data collected in the BMD Substudy will be reviewed by the VOICE Protocol Safety Review Team (PSRT) and the NIAID Vaccine and Prevention Data Safety Monitoring Board (DSMB), together with all other VOICE Study safety data, as outlined in Section 8.1 of the VOICE Protocol.

Following completion of VOICE, the site IoRs will notify the MTN-003B Protocol Team with any unexpected safety concerns. No DSMB oversight or MTN Study Monitoring Review is planned for this study following completion of VOICE. The protocol team will conduct periodic internal reviews of study progress, including rates of participant retention. These reviews will take place every 3 months.

# 8.2 Adverse Events Definitions and Reporting Requirements

An adverse event (AE) is defined as any untoward medical occurrence in a clinical research participant administered an investigational product and which does not necessarily have a causal relationship with the investigational product. As such, an AE can be an unfavorable or unintended sign (e.g., an abnormal laboratory finding), symptom, or disease temporally associated with the use of an investigational product, whether or not this sign is considered product related. AEs will be identified, documented, reported, and managed in the VOICE Study as outlined in Section 8.2 of the VOICE Protocol. In addition, for VOICE participants who take part in the BMD Substudy, bone mineral loss (grade 2 or higher) will be reported as an AE. The severity of AEs involving bone mineral loss will be graded according to Table 2 below. The relationship of AEs involving bone mineral loss will be assessed based on the Manual for Expedited Reporting of Adverse Events to DAIDS, dated January 2010 (DAIDS EAE [expedited adverse event] Manual), the VOICE Study oral product Package Inserts and the clinical judgment of the IoR designee. The study products that must be considered when AE relationships are specified are the TDF tablet and the FTC/TDF tablet.

Bone Mineral Loss			
GRADE 1 MILD	GRADE 2 MODERATE	GRADE 3 SEVERE	GRADE 4 POTENTIALLY LIFE-THREATENING
BMD T-score -2.5 to -1.0			Pathologic fracture causing life-threatening consequences
BMD Z-score -2.0 to -1.0			Pathologic fracture causing life-threatening consequences

Following participant completion of the VOICE PUEV, any AEs identified during an MTN-003B visit, including bone mineral loss of any grade, will not be reportable (unless the participant is co-enrolled in another MTN trial, in which case the other trial's AE reporting guidelines apply).

# 8.3 Expedited Adverse Event Reporting Requirements

The EAE reporting requirements and definitions for this substudy are the same as those outlined in Section 8.3 of the VOICE protocol, except that the study agents considered in determining relationships of AEs requiring expedited reporting are the TDF tablet and FTC/TDF tablet.

# 8.4 Regulatory Requirements

Information on all reported AEs will be included in reports to the US Food and Drug Administration (FDA) and other applicable government and regulatory authorities. Site IoRs/designees will submit AE information in accordance with local regulatory agencies' or other local authorities' requirements. Site IoRs/designees will also submit AE information and any other relevant safety information to their Institutional Review Boards (IRBs)/Ethics Committees (ECs) in accordance with IRB/EC requirements.

# 8.5 Social Harms Reporting

The social harms reporting requirements and definitions for this substudy are the same as those outlined in the VOICE protocol.

# 9 CLINICAL MANAGEMENT

In addition to those listed in Section 9 of the VOICE protocol, guidelines for clinical management and product temporary hold/permanent discontinuation for the BMD Substudy are outlined in this section.

## 9.1 BMD Status: Baseline

- For participants with a baseline BMD < -2.0 SD Z-score (ages 18 to 29 years) or T-score < -2.0 SD (ages 30 and older), the IoR/designee will be required to do the following:
  - Discuss options for treatment or prevention of osteoporosis with the study participant. The study will provide calcium supplementation if recommended by the IoR/designee.

## 9.2 BMD Status: During Follow-up

For participants with more than a 1 SD reduction in BMD compared to baseline, the IoR/designee should repeat the DXA scan as soon as possible and consult the PSRT.

For participants with Z-scores (ages 18-29) or T-scores (age  $\geq$ 30) less than -2.0 SD during follow-up the IoR/designee will be required to do the following:

 Discuss options for treatment or prevention of osteoporosis with the study participant. The study will provide calcium supplementation if recommended by the IoR/designee.

## 9.3 BMD Status: Following Participant Completion of the VOICE PUEV

For participants with more than a 1 SD reduction in BMD compared to baseline, the IoR/designee should repeat the DXA scan, if not previously done.

For participants with Z-scores (ages 18-29) or T-scores (age  $\geq$ 30) less than -2.0 SD compared to baseline, the IoR/designee will be required to do the following:

o Discuss options for treatment or prevention of osteoporosis with the study participant. The study will provide calcium supplementation if recommended by the IoR/designee.

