#### MTN-003B

#### Bone Mineral Density Substudy to MTN-003 (VOICE)

#### PROTOCOL SUMMARY

Short Title:	BMD Substudy	
IND Sponsor:	Division of AIDS, NIAID, US NIH	
Chair:	[name], MPH	
Sample Size:	All eligible participants	
Study Population:	Sexually active, HIV-uninfected women 18 to 45 years old who have been randomized to oral study product in MTN-003 [VOICE (Vaginal and Oral Interventions to Control the Epidemic)], and elect participation in the Bone Mineral Density (BMD) Substudy.	
Study Sites:	VOICE Study sites selected by the MTN Executive Committee	
Study Design:	Observational substudy of VOICE	
Study Duration:	Approximately 48 months total. Accrual will require approximately 21 months. Follow-up will continue 12 months after the VOICE Product Use End Visit (PUEV).	

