## BMD

In a clinical setting, BMD test results are typically compared to the average bone density of young, healthy adult peak bone mass (T-score) and to the average bone density of other people of the same age, sex, and race (Z-score). For women, the classification of osteoporosis using DXA measurements of BMD is currently based on the T-score if they are age 30 or older. For women under age 30, the Z-score is used (comparison to agematched) since peak bone mass has not yet been reached. In the BMD Substudy, we will look for changes in BMD in women taking the oral study products used in VOICE.

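### Section 9.3 ties the post-PUEV -2.0 SD trigger for the osteoporosis discussion to the woman's own baseline, unlike 9.1, 9.2 and the score definitions in 2.4 (minor, wrong as written)

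*Protocol*

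**What the plan says.** Section 9 of the Protocol sets the same required action at three stages: discuss options for treating or preventing osteoporosis, with calcium supplied if the investigator recommends it. All three stages use the Z-score for ages 18 to 29, the T-score from age 30, and the cut-off -2.0 SD.

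- Section 9.1, at baseline: "For participants with a baseline BMD < -2.0 SD Z-score (ages 18 to 29 years) or T-score < -2.0 SD" from age 30.
- Section 9.2, during follow-up: a score "less than -2.0 SD during follow-up the IoR/designee will be required to do the following".
- Section 9.3, after the PUEV: a score "less than -2.0 SD compared to baseline, the IoR/designee will be required to do the following".

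Section 9.3 also has a first rule, directly above: a reduction in BMD of more than 1 SD from baseline calls for a repeat DXA scan if none has been done.

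Section 2.4 gives the reference for each score. The T-score compares with young, healthy adult peak bone mass, and the Z-score with people of the same age, sex and race. Section 10.5.1 has the DSMB watch for Z-scores below -2.0 in women aged 18 to 29, again without reference to baseline.

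**The concern.** A Z- or T-score is already a comparison with a reference population. Adding a comparison with baseline either makes the rule a different one, a fall of more than 2 SD from the woman's own first scan, or leaves its meaning uncertain. The Protocol gives no reason for a new basis after the PUEV. The phrase was probably carried down from the 1 SD rule above it, though that is inference.

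At stake is a required protective action for an individual participant. A site that follows the words literally would not be obliged to hold the discussion with a woman whose score first drops below -2.0 in the year after product use. The Protocol relies on fewer other checks in that year. Under Section 8.2, adverse events found after the PUEV, "including bone mineral loss of any grade, will not be reportable", unless the woman is co-enrolled in another MTN trial. Section 8.1 adds: "No DSMB oversight or MTN Study Monitoring Review is planned for this study following completion of VOICE".

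**Working it through.** The Protocol states no figure for this rule, so the check compares the triggers and then sizes the literal one.

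**Step 1. The triggers side by side.** Let *b* be the baseline score and *f* the score at a visit after the PUEV.

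- Absolute trigger (9.1, 9.2, and the DSMB criterion for ages 18 to 29): *f* < -2.0.
- Literal 9.3 trigger: *f* - *b* < -2.0.
- Repeat-scan rule in 9.3: *b* - *f* > 1.

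**Step 2. The case with a practical consequence.** Take *b* = -1.8 and *f* = -2.2.

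- Absolute: -2.2 < -2.0, so the discussion is required.
- Literal: -2.2 - (-1.8) = -0.4, which is not below -2.0, so it is not required.
- Repeat scan: the fall is 0.4 SD, which is less than 1, so it is not triggered.

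Read literally, Section 9.3 asks for nothing on this scan.

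**Step 3. How large a fall the literal rule needs.** Section 10.4 gives baseline means of 1.0 to 1.2 g/cm² and SDs of 0.1 to 0.2 g/cm². The Protocol does not give the reference SD behind the scores, so the 10.4 SD is used in its place (assumption). The required fall as a share of BMD is 2 × SD / mean:

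- smallest: 2 × 0.1 / 1.2 = 16.7%
- largest: 2 × 0.2 / 1.0 = 40%

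For comparison, Section 2.4 reports a loss of about 1% against placebo in HIV-negative men on tenofovir after 24 to 48 weeks.

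**Step 4. How often it would fire.** Assume normally distributed percentage change with the 4.5% SD of Section 10.4. That SD is set for 12 months, but the same section cites 3.5% to 4.6% through 144 weeks, so it is a fair stand-in for a longer span. Take a mean change between 0 and -2.1%, the latter being the Protocol's detectable difference. At the smallest threshold:

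- mean 0: P(Z < -16.7 / 4.5) = P(Z < -3.70) ≈ 0.0001
- mean -2.1%: P(Z < (-16.7 + 2.1) / 4.5) = P(Z < -3.24) ≈ 0.0006

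Every other combination of the 10.4 mean and SD gives a smaller value. Even with 540 women, the upper end of planned enrolment, 540 × 0.0006 ≈ 0.3 women would be expected to meet the literal rule at a given scan and skeletal site.

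**Step 5. After the correction.** With the three words deleted, the 9.3 trigger is *f* < -2.0. The woman in Step 2 then requires the discussion, as she would have before the PUEV.

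**The case against.** The strongest reply is that no clinician would read the rule literally. A Z- or T-score is by definition a comparison with a reference population; the age split, cut-off and action match 9.1 and 9.2; and the rule just above uses the word 'reduction' when change is meant, while this one does not. That the literal rule would almost never fire makes it less likely still that a site would adopt it. All of this stands, and it is why the point is minor. It does not correct the text, and no other section does.

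A second reply is that Section 9.2 may already cover the gap. It applies during follow-up, and Section 7.3 says: "The follow-up visits will occur at 6 months and 12 months following the VOICE PUEV". No sentence ends 9.2 at the PUEV. This too is a fair argument, but the separate heading of 9.3, and its own modified version of the 1 SD rule, suggest that 9.3 takes over. The Protocol does not say which rule governs.

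A reader might infer that the rules give opposite required actions for the same scan. They do not: the readings differ only between required and not required, and nothing forbids the discussion. A site that always holds it when the score is below -2.0 breaches nothing by doing so. A reader might also point to the reverse mismatch, such as a fall from +0.6 to -1.5 (2.1 SD), where only the literal rule requires the discussion. The sizes in the working make that practically unreachable. Nor does a woman already below -2.0 before the PUEV lose anything: Sections 9.1 and 9.2 had already required the discussion.

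**Conclusion.** The second rule of Section 9.3 is wrong as written and the severity is minor. It conflicts with 9.1, 9.2 and the score definitions in 2.4, and it leaves the required discussion ambiguous for one group: women who first cross -2.0 after the PUEV with a fall of 2 SD or less. Their number cannot be estimated from the Protocol. It is likely small, because Section 2.2.1 expects baseline BMD to be normal or higher than average.

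The textual conflict rests on no assumption. The 17% to 40% size rests on using the 10.4 SD as the score unit, and the probability of at most about 0.0006 rests in addition on the normal model and the 4.5% SD.

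It would be tempting to present this as a demonstrated safety gap because adverse-event reporting of bone loss stops after the PUEV and DSMB oversight ends when VOICE is complete. The documents do not support that. Section 10.5.1 explains the end of DSMB oversight by the absence of further product exposure, Section 8.1 still has investigators notify the protocol team of unexpected safety concerns, and the 1 SD repeat-scan rule remains. No endpoint, sample size, error rate or analysis is affected.

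**What to change.** In the second rule of Section 9.3, delete 'compared to baseline', or replace it with 'at a visit after the PUEV'. Keep the phrase in the 1 SD repeat-scan rule, where a change from baseline is meant. A current score below -2.0 is then the trigger in 9.1, 9.2 and 9.3, and it no longer matters for this action whether 9.2 continues past the PUEV. The cost is a clarification memo or letter of amendment covering three words, with no change to visits, scans, data collection or analysis.
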